10.0 STUDY CALENDAR

	Baseline	Post-Consult	Mid way through RT	End of treatment visit	Follow up
	-4 weeks of Registration	After consult and prior to treatment	Fraction 2 or 3 ^A	30 ± 7 days post last treatment	3, 6, and 12-month post-RT
Informed Consent	X				
History	X				
Physical	X				X ^B
Vitals (ht, wt, bp)	X				X
Clinical Assessment			X ^C		
ECOG score	X				X
CBC w/ diff, platelets, CMP, INR	X		X ^D	X	X
AFP or CEA as indicated	X				X
Urine pregnancy test	X ^E				
CTP, MELD, and ALBI scores	X		X		
CT Simulation Scan		X			
MRI with Eovist of abdomen and/or Triple Phase ABD CTG		X ^F			X
HIDA scan		X ^F	X		X

^A Subjects who have a total of 3 fractions will have Midway Assessments done at fraction 2. Subjects who have a total of 5 fractions will have Midway Assessments at fraction 3.

^B Physical Exam required for Follow up visits. History not required.

^C Subjects will be seen at least once per week during their course of RT for clinical assessment. This will include a limited physical exam and toxicity assessment.

^D Labs may be monitored more frequently per the treating physician's discretion.

^E Only required in female subjects of child bearing potential

^F HIDA or Eovist MRIs obtained prior to consult can be used if performed within 8 weeks of simulation.

^G Imaging evaluation to be determined by treating MD depending on patient's clinical situation. For Ex: some patients may have a contraindication to a certain imaging modality (e.g. CT contract allergy). As long as the patient undergoes follow-up imaging, the use of CT vs. MRI for imaging follow up will not be considered a protocol deviation

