1.0 SCHEMA

2.0 BACKGROUND

Liver malignancies, especially hepatocellular carcinoma (HCC), often arise in patients with cirrhosis, who exhibit significant variability in their liver function. The primary methods of assessing the severity of cirrhosis are clinical scoring systems such as the Child-Turcotte-Pugh (CTP) score or the Modified End-Stage Liver Disease (MELD) score. The Barcelona Clinic Liver Cancer (BCLC) staging, Cancer of the Liver Italian Program (CLIP) score, and the newest albumin-bilirubin (ALBI) grade have been proposed as alternative ways to assess the severity of liver dysfunction. Patients with liver tumors who need radiation may not be diagnosed with cirrhosis but may have significant alteration in their liver function due to prior chemotherapy or other local therapy. The gold standard lab test for global liver function evaluation is indocyanine green retention at 15 minutes (ICG15). However, one of the most clinically important limitations of all these tests is the lack of information that they provide regarding regional variations in hepatic function within the liver of an individual patient, which are increasingly well described. Such regional variability can have important implications for radiation treatment (RT) planning, delivery, and outcome assessment in patients with liver cancer. Recently, visualizing regional differences in hepatic function has become possible with the development of imaging techniques using technetium-99m (Tc99m) hepatobiliary iminodiacetic acid (HIDA) scans, Tc99m galactosyl human serum albumin (GSA) scans, dynamic contrast enhanced (DCE) computed tomography (CT), DCE magnetic resonance imaging (MRI), and functional MRIs (fMRIs) using contrast agents such as Eovist. Theragnostic imaging is the application of quantitative information from imaging studies to guide therapeutic interventions. These technologies therefore may have important applications in RT for liver cancer as they can provide a “road map” for how to design radiation plans to avoid functioning liver.

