5.0 ELIGIBILITY CRITERIA

5.1 Inclusion Criteria

1. Subjects must be ≥ 18 years of age at the time of signing informed consent
2. Diagnosis of primary liver malignancy (including hepatocellular carcinoma [HCC] or cholangiocarcinoma) or liver metastasis from any primary solid tumor site by characteristic imaging findings on CT or MRI, clinical presentation, and/or pathologic confirmation of diagnosis. Subjects with other current or prior malignancies are eligible for this study.
3. Patients with liver metastases must have at least one of the following clinical factors that may affect liver function:
 - a. History of liver resection (at any time)
 - b. History of cirrhosis (any cause), fatty liver disease, or hepatic insufficiency due to any cause
 - c. Prior radiation to the upper abdomen including radioembolization
4. ECOG (Zubrod) Performance Status 0-2.
5. Subjects must have a Child-Turcotte-Pugh (CTP) score ≤ 7 to be eligible.
6. Patients who have been previously treated with non-SBRT liver directed therapies may be enrolled on study. At least 3 months must have elapsed between the most recent liver-directed therapy and study entry.
7. Ability to provide written informed consent and HIPAA authorization
8. Subjects with an allergy to contrast agents may be enrolled at the treating physician's discretion with appropriate pre-treatment and symptom management.

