5.2 Exclusion Criteria

1. Subjects who are pregnant or planning to become pregnant during the study. Women of child bearing potential must have a negative pregnancy test
2. Subjects must not have received chemotherapy within 2 weeks of planned 1st day of RT.
3. No more than 3 lesions may be treated. The maximum sum of the diameter(s) of the lesion(s) must be ≤ 6 cm
4. Uncontrolled intercurrent illness including, but not limited to, ongoing or active infection (or infections requiring systemic antibiotic treatment), active upper GI ulceration or hemorrhage, symptomatic congestive heart failure, unstable angina pectoris, cardiac arrhythmia, or psychiatric illness/social situations that would in the opinion of the investigator limit compliance with study requirements

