8.2 Simulation Period

After subjects have been found eligible and enrolled to this study, each subject will undergo CT simulation for SBRT treatment planning. Two radiation treatment plans will be created for each subject and compared. The plan which best spares functional liver while maintaining adequate target coverage will be selected for each subject. Within 8 weeks of the simulation, the subject should have the following functional scans for enrollment:

1. HIDA scan
2. MRI with Eovist contrast (fMRI)

If a patient cannot obtain an MRI or refuses to undergo eovist MRI, the subject may be enrolled on the study at the discretion of the principal investigator.

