8.3 Radiation Treatment Period

During radiation treatment, subjects will be seen at least once per week for clinical assessment that will include a limited physical exam and assessment of toxicity.

Midway through radiation treatment, subjects will have the following procedures:

1. Laboratory Assessments (CBC with differential, CMP, INR) for assessment of CTP, MELD, and ALBI scores.
2. HIDA scan

Subjects who have a total of 3 fractions will have Midway Assessments done after fraction 2. Subjects who have a total of 5 fractions will have Midway Assessments after fraction 3.

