13.8 Analysis of Exploratory Objectives

To assess the correlation between the radiation dose and the risk of RILD, graphs and descriptive statistics will be used to see if any relationships may exist.

Spearman's correlations will be used to compare output from each of the HIDA and fMRI scans to see if any measures correlate to each other.

To assess significant change in HIDA and fMRI scans, the plan based off the HIDA scan done at mid-therapy would be re-optimized, retrospectively. The proportion of patients who have a change in the regional distribution of function after the initial radiation treatments will be determined. If this re-optimized plan reduces the functional liver exposed to <15 Gy by 5% or more, this would be considered significant and will provide a potential idea about the feasibility of potential adaptive radiotherapy.

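### The mid-treatment HIDA change and adaptation rate in section 13.8 can also reflect drift or chemotherapy before RT, because the planning scan may be 8 weeks old at simulation

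*Combined protocol and SAP*

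**What the plan says.** All references are to the combined protocol and SAP.

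- **Age of the planning scan.** Section 8.2: "Within 8 weeks of the simulation, the subject should have the following functional scans for enrollment". Footnote F of section 10.0 allows reuse of older scans: "HIDA or Eovist MRIs obtained prior to consult can be used if performed within 8 weeks of simulation". The calendar has no other HIDA scan before RT, and no maximum time from simulation to first fraction is given.
- **Chemotherapy.** Section 5.2, item 2: "Subjects must not have received chemotherapy within 2 weeks of planned 1st day of RT". The washout is counted back from RT, not from the scan.
- **Mid-treatment scan.** Section 8.3: "Subjects who have a total of 3 fractions will have Midway Assessments done after fraction 2". With 5 fractions it follows fraction 3. Section 9.4 sets at least 48 hours between fractions and allows weekly spacing.
- **Analysis.** Section 13.8: "The proportion of patients who have a change in the regional distribution of function after the initial radiation treatments will be determined". The plan is then re-optimised retrospectively on the mid-treatment scan. A 5% gain counts as significant and is taken to bear on the feasibility of adaptive radiotherapy. Neither scan age nor therapy given between the scans is mentioned.
- **Prior therapy and liver function.** Section 2.0 says that patients "may have significant alteration in their liver function due to prior chemotherapy or other local therapy".

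**The concern.** Section 13.8 compares two HIDA maps and places the change after the first fractions. The earlier map, however, need not describe the liver at the first fraction. If it is weeks old, and chemotherapy has been given since, the difference between the maps combines three things: change before RT without treatment, change from chemotherapy, and change from radiation. The analysis cannot separate them.

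This matters for what is concluded. The Background motivates adaptation by a during-treatment HIDA scan that picks up individual sensitivity to radiation. If the map was already out of date at the first fraction, the lesson is that the baseline scan should be fresher. If it changed during radiation, the lesson is that mid-course adaptation may be worth studying. As written, the first situation could be reported as support for the second.

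**Working it through.** The plan gives no figure on this point. Its probability table in section 13.4 concerns the primary 3-of-15 rule and is not involved. The check is calendar arithmetic.

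**Inputs**
- Planning scan to simulation: at most 8 weeks = 56 days (8.2; 10.0, footnote F).
- Chemotherapy-free period before the first fraction: 14 days (5.2, item 2).
- Simulation to first fraction, *g*: not stated. Assumed 0 to 21 days.
- First fraction to mid-treatment scan, *r*, taking the scan on the day of the stated fraction (8.3, 9.4). For fraction 2 of 3, one gap: 2 days at 48-hour spacing, 7 days if weekly. For fraction 3 of 5, two gaps: 4 days at 48-hour spacing, 14 days if weekly. So *r* runs from 2 to 14 days.

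**Formulas at the 8-week limit**
- Days after the planning scan on which chemotherapy is permitted: 56 + *g* − 14 = 42 + *g*.
- Days between the two HIDA scans: 56 + *g* + *r*.
- Share of that interval after the first fraction: *r* / (56 + *g* + *r*).

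| *g* (assumed) | Days open to chemotherapy | Days between scans | Share after first fraction |
|---|---|---|---|
| 0 | 42 | 58 to 70 | 2/58 = 3.4% to 14/70 = 20.0% |
| 7 | 49 | 65 to 77 | 2/65 = 3.1% to 14/77 = 18.2% |
| 14 | 56 | 72 to 84 | 2/72 = 2.8% to 14/84 = 16.7% |
| 21 | 63 | 79 to 91 | 2/79 = 2.5% to 14/91 = 15.4% |

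For such a subject, roughly 80% to 97% of the time between the scans lies before any radiation. The exposure shrinks with a fresher scan: if the scan is *s* days before simulation, the open period is *s* + *g* − 14 days, which is nil once the scan is within 14 days of the first fraction.

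**Effect on the rate.** With the target of 15 evaluable subjects (13.4), one subject counted for a change that arose before RT moves the rate by 1/15 = 6.7 points. As an illustration with assumed rates only: if 10% to 30% of subjects changed for reasons other than radiation and none from radiation, 15 × 0.10 = 1.5 to 15 × 0.30 = 4.5 subjects would still count as changed.

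**Liver-directed therapy.** Section 5.1, item 6: "At least 3 months must have elapsed between the most recent liver-directed therapy and study entry". Section 8.2 puts simulation after entry: "After subjects have been found eligible and enrolled to this study, each subject will undergo CT simulation for SBRT treatment planning". Taking 3 months as 91 days and simulation on the day of entry, the oldest permitted scan is 91 − 56 = 35 days after that therapy; later simulation lengthens the gap. Liver-directed therapy given before entry therefore cannot fall between the two scans.

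**The case against.** The strongest reply is that the endpoint does not claim a radiation cause. Objective 3 in section 4.3 concerns change midway through treatment, and endpoint 3 in section 4.6 asks only how often the plan might have been adapted. If the map differs for any reason, a new plan might spare more liver, so the rate is correct as defined. That stands. What remains is interpretation: section 13.8 draws a tentative inference about adaptive radiotherapy, and that inference depends on when the change arose.

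Second, a reader might infer that the adaptation rate is biased upward. The documents do not show this. The Background remark concerns liver function after prior treatment; it does not say that a few weeks of chemotherapy alter the regional map. The contours in section 9.4 are percentages of maximum uptake, so a uniform change across the liver would leave them as they are. A regional drug effect is possible but not demonstrated.

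Third, a reader might extend the point to liver-directed therapy or to the primary endpoint. The first fails on the dates worked through above. On the second, sections 4.4 and 9.1 compare both plans for one subject on the same functional data, so an older map does not favour either plan by construction and the contrast is little affected.

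Fourth, 42 to 63 days is an upper limit. The calendar places the HIDA scan after consult and before treatment, with reuse of earlier scans as an allowance, and nothing says how many subjects will combine an old scan with later chemotherapy. That also stands.

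**Conclusion.** The concern holds as a minor point about interpretation and reporting. The documents permit at least 42 days of possible chemotherapy after an 8-week-old planning scan (up to 63 with an assumed 21-day gap to RT), against about 2 to 14 days of radiation before the second scan. The change and adaptation rate in 13.8 can therefore also reflect drift or chemotherapy before RT, and the planned analysis offers no means of telling these apart from change during radiation.

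The day counts rest on the 8-week limit, the assumed range for simulation to RT, and a mid-treatment scan on the day of the stated fraction. The size of any distortion cannot be estimated, because neither the number of affected subjects nor the regional effect of chemotherapy is known. The endpoint is exploratory and descriptive, has no decision rule that depends on the source of the change, and does not enter the 3-of-15 rule. The documents do not support a conclusion that the rate is known to be inflated or that the primary comparison is compromised.

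**What to change.** Amend section 13.8 as follows:

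1. Describe the result as change since the planning HIDA scan.
2. Report the proportion with change and the adaptation rate overall, and separately in subjects with no systemic therapy between the planning scan and the mid-treatment scan.
3. List the remaining subjects individually, with the number of days from planning scan to first fraction. Summarise that interval for the no-therapy group too, since the split removes chemotherapy but not scan age.
4. Base any statement about adaptive radiotherapy on the no-therapy group.

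**Cost.** The scan dates will be on file, and the last chemotherapy date is already needed to apply exclusion criterion 2; a last date later than the planning scan identifies chemotherapy given between that scan and RT. The calendar schedules a history only at baseline, so the date, and any systemic therapy not counted as chemotherapy, should be confirmed up to the mid-treatment scan. The main downside is a smaller denominator, and so a less precise rate, for one exploratory endpoint. No visit or scan is added.

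A new rule restricting which planning scans may be used is not needed for this purpose. It could force repeat scans or lose subjects, which is a trade-off that this exploratory endpoint does not justify.

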11.0 TOXICITIES TO BE MONITORED/DOSAGE MODIFICATIONS

All subjects will have laboratory evaluation prior to initiation of treatment. This includes CBC with differential, platelets, CMP, and INR.. Radiation treatment will be suspended in subjects who develop new ascites (as indicated by abdominal ultrasound, CT scan, or physical exam) or encephalopathy. If the patient's clinical status is borderline and the treating physician determines a treatment break is necessary, re-evaluation for further treatment can occur 1-2 days later.

	CTP-A	CTP-B7
Total Bilirubin	<3	<4
Albumin	>2.5	>2.5
INR	<1.5X upper normal	PT > 6 seconds above normal
ANC	>1000	>1000
Platelets	>50,000	>50,000
Hgb	>9	>9
Ascites	none	none
Encephalopathy	none	none

The subject will be seen at least once weekly during treatment for assessment of side effects. The most current version of Common Terminology Criteria for Adverse Events (CTCAE) will be used for grading toxicity.

For the purposes of this study, we will monitor the following:

- Labs: AST, ALT, Alkaline phosphatase, bilirubin, INR, platelets, albumin, lymphocytes, sodium
- Hepatobiliary disorders: hepatic failure, hepatic hemorrhage, hepatic necrosis, hepatic pain, perforation of bile duct, portal hypertension, portal vein thrombosis, bile duct stenosis, biliary fistula, cholecystitis, gallbladder fistula
- Gastrointestinal disorders: ascites, duodenal hemorrhage, duodenal obstruction, duodenal perforation, duodenal stenosis, duodenal ulcer, gastric necrosis, gastric perforation, gastric stenosis, gastric ulcer
- Nervous system disorders: encephalopathy
- Musculoskeletal and connective tissue disorders: chestwall pain
- Renal and urinary disorders: acute kidney injury

A copy of the most current CTCAE version is available at <http://ctep.cancer.gov/reporting/>

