Significant variability in liver function is present in the population of patients with liver tumors and cirrhosis. Different models for grading the severity of cirrhosis are available, including the Child-Turcotte-Pugh (CTP) and Model for End-Stage Liver Disease (MELD) score. To date, CTP score has been the preferred scoring system in evaluating patients for consideration of SBRT. There are other staging and prognostic scores for patients with HCC including the AJCC stage, BCLC stage, CLIP score, and ALIBI score. The CTP score is based on the levels of bilirubin, albumin, and PT/INR; it also incorporates a subjective grading system for ascites and encephalopathy. The range of scores is 5 to 15, with scores 5-6 classified as CTP A, 7-9 CTP B, and 10-15 CTP C.[13] The risk of side effects has been suggested to increase with higher CTP scores. In the study by Choi et al, 75% of their patients had CTP A disease, and there were no grade 3 toxicities reported in their trial. [11] One-third of patients in the phase I/II trial at Indiana University experienced grade 3 hematologic or hepatic toxicity, although 17 out of 21 of those patients had pre-treatment grade 2 dysfunction in that category. In addition, there were 4 patients who had progressive liver dysfunction, 2 of whom went on to liver transplantation and the other 2 who died as a result of liver failure. All 4 of these patients had CTP \geq B8, and 2 of those patients were treated with 42 Gy in 3 fractions, which was concluded to be unsafe in CTP B patients.[10]

In addition to baseline liver dysfunction, many of the patients who are referred for liver SBRT have had prior therapies such as surgical resection, chemotherapy, RFA, TACE, or conventional radiotherapy, which can adversely affect liver function. A recent retrospective study from Michigan comparing their institutional experience of SBRT with RFA found that patients who were treated with SBRT were more likely to have received prior liver-directed therapies with a median of 2 treatments in SBRT patients compared to 0 in RFA patients.[14]

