Currently, standard constraints for liver SBRT planning stipulate that 700 cc of “uninvolved liver”, i.e., the volume of liver minus the gross tumor volume (GTV), should receive <15 Gy. This constraint is derived from a phase I study conducted at the University of Colorado (which itself was based on surgical data showing that 75-80% of the liver can be safely resected).[9, 17] Since 25% of the assumed average liver volume of 2000 cc is 500 cc, 700 cc was used as a conservative limit. The basis for 15 Gy was that its BED is 40 Gy₃ which is less than the whole liver tolerance of 49.5 Gy₃ as determined from an early RTOG dose escalation study of whole liver RT.[18] The current constraint does not take into account the functional residual capacity of the untreated liver. However, information about regional variations in liver function could help to evaluate the safety of RT in patients who are borderline candidates for liver RT based on their liver function. In this protocol, we will meet the standard physical constraints but plan to increase safety further by attempting to decrease dose to functional areas.

The indocyanine green (ICG) retention study is presently the gold standard for assessing liver function, but this study only provides information about global liver function.[19] An ICG retention at 15 minutes (ICG15) of less than 14% has historically been used as a cutoff to select patients for major hepatectomy, but subsequent trials have shown that well-selected patients with ICG15 values above this cutoff had similar outcomes as those with lower ICG15 values[20, 21] According to the 2016 NCCN hepatobiliary guidelines, ICG15 is widely used in Asia but not in Western countries. Two studies from the University of Michigan reported baseline ICG values in patients’ pre-treatment. They reported ICG clearance as ICG half-life, whereas the surgical data looks at ICG retention at 15 minutes (ICG15). In a total of 29 patients, the values ranged from 3.75 minutes to 14.5 minutes, which would correlate with an expected ICG15 of 6.25% to 48.8%. In this study, 14 of 29 (48.3%) of patients would have had a ICG value >14%. Clearly, the patients undergoing radiation therapy for liver tumors can have a large variation in their liver function. Having more data as to what functional residual capacity correlates with the ability to safely deliver radiation therapy would be beneficial.

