8.4 End of Treatment Visit

Lab assessment should be performed within 30 (+/-7) days from last radiation treatment. This includes at least CBC with diff, CMP, INR

- 1.

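### Section 11 table: the CTP-B7 clotting cell states the abnormal side, so as printed these subjects have no numeric clotting ceiling

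*Combined protocol and SAP*

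**What the plan says.** Section 11.0 requires blood tests before treatment and then sets out a table by CTP class. In the clotting row, labelled INR, the CTP-A cell is "<1.5X upper normal" and the CTP-B7 cell is "PT > 6 seconds above normal". The table has no caption, and no sentence says what follows if a value is not met. The explicit stopping rule is in the text above it: "Radiation treatment will be suspended in subjects who develop new ascites", with encephalopathy as the other trigger. The same paragraph lets the treating physician call a break when clinical status is borderline.

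The entry rule in section 5.1 concerns only the total score: "Subjects must have a Child-Turcotte-Pugh (CTP) score ≤ 7 to be eligible". Section 2.0 describes that score: "The CTP score is based on the levels of bilirubin, albumin, and PT/INR; it also incorporates a subjective grading system for ascites and encephalopathy". On its scale, it says "The range of scores is 5 to 15", with 7 to 9 classed as CTP B. With entry capped at 7, the CTP-B7 column therefore covers subjects scoring exactly 7.

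**The concern.** A table of this kind is useful only if every cell can be read the same way. A coordinator checking a CTP-B7 subject row by row finds seven values that the subject should satisfy and one that the subject should presumably not satisfy. Read like its neighbours, the clotting cell asks for a prolonged prothrombin time and sets no upper bound on it.

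It falls in the column for subjects with the poorer liver function of the two groups. It is also the only place in the protocol where a clotting limit for them could be found. What is at stake is whether the written table can work as a clotting check for these subjects. The analysis is not at stake.

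**Working it through.** The plan gives no calculated figure for this cell, so the check compares the cells with one another and searches for a limit elsewhere.

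**1. Direction of each cell (section 11.0 table).** 8 rows × 2 columns = 16 cells.

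| Row | CTP-A | CTP-B7 | What the cell states |
|---|---|---|---|
| Total bilirubin | <3 | <4 | acceptable, ceiling |
| Albumin | >2.5 | >2.5 | acceptable, floor |
| Clotting (row labelled INR) | INR below 1.5 × upper normal | PT more than 6 s above normal | A: acceptable, ceiling; **B7: abnormal side** |
| ANC | >1000 | >1000 | acceptable, floor |
| Platelets | >50,000 | >50,000 | acceptable, floor |
| Hgb | >9 | >9 | acceptable, floor |
| Ascites | none | none | acceptable |
| Encephalopathy | none | none | acceptable |

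Acceptable cells: 3 ceilings (two bilirubin, one INR) + 8 floors (albumin, ANC, platelets, Hgb, two each) + 4 entries of none = 15. Abnormal side: 16 − 15 = 1. The contrast is between acceptable and abnormal values, not between symbols: eight of the acceptable cells also use a greater-than sign, correctly, because low values are the harmful ones there.

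**2. Can another reading rescue the table?**
- As conditions to treat: 15 cells make sense and the CTP-B7 clotting cell does not.
- As conditions to hold: the CTP-B7 clotting cell makes sense and the other 15 do not.
- As a description of the CTP classes: ANC, platelets and Hgb are not among the five CTP items in section 2.0, so the table is not a class definition.

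The first reading needs one correction and the second needs fifteen.

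**3. Is there a ceiling elsewhere?** Sections 8.1, 8.3, 8.4 and 8.5 and the calendar in section 10.0 schedule INR but attach no limit to it. The suspension text in section 11.0 names new ascites and encephalopathy only.

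**4. Does the entry limit stand in for a ceiling?** Inputs: five CTP items, range 5 to 15 (section 2.0), entry at 7 or below (section 5.1). Assuming equal weights, each item runs from 5/5 = 1 to 15/5 = 3 points.
- Worst clotting score, best score on the other four: 3 + 4 × 1 = 7, which is eligible and falls in the CTP-B7 column.
- If clotting could score at most 2: 2 + 2 + 1 + 1 + 1 = 7, again with the worst clotting score and again eligible.

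The total score therefore does not limit clotting. Moreover, if absent ascites and encephalopathy score 1 each, a subject meeting those two rows reaches 7 only through bilirubin, albumin or clotting (7 − 2 = 5 points over three items with a minimum of 3). Clotting is one of three possible sources of the two extra points.

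**5. Does the design depend on this?** Section 13.4 uses P(X ≥ 3) for X binomial with n = 15. At true rates 0.1, 0.2, 0.25, 0.3, 0.4 and 0.5 this gives 0.184, 0.602, 0.764, 0.873, 0.973 and 0.996, matching the printed 0.18, 0.60, 0.76, 0.87, 0.97 and ≥ 0.99. No clotting value enters.

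**6. After the correction.** With the inequality reversed, 16 of 16 cells state an acceptable value and CTP-B7 has a written ceiling.

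**The case against.** The strongest reply is that the practical effect is slight and largely inferred. The table has no caption and no action, so nothing in the text says that the cell governs starting, holding or resuming treatment. The neighbouring CTP-A cell is plainly a ceiling, and a clinician is unlikely to read the CTP-B7 cell as a demand for prolonged clotting. INR is measured before and midway through treatment, and subjects are seen at least weekly. The physician may order a break (section 11.0) or withdraw a subject for safety (section 12.0), and the monitoring committee reviews summaries monthly (section 16.0). All of this stands and keeps the point minor. None of it is a numeric ceiling.

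The intended sign and cut-off are also inferred. A character error in the published file cannot be excluded, although the rest of the row is intact. This limits what can be said about the sponsor's intent, but not about the inconsistency as printed.

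Two stronger readings are tempting and not supported:
- A reader might infer that CTP-B7 subjects would be irradiated whatever their clotting, or that prolonged clotting is required for treatment. The table states no action, and the discretion described above remains.
- A reader might infer that the cell cannot be applied because the protocol measures only INR. Section 2.0 writes the two measures together, and the end-of-treatment list is a minimum: "This includes at least CBC with diff, CMP, INR". PT may well be available. The switch from INR to PT within the row is only a mismatch of units.

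**Conclusion.** The point holds as a minor error in a safety table. One of 16 cells states the abnormal side. As printed, CTP-B7 subjects have no numeric clotting ceiling, and neither another section nor the entry limit provides one.

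The inconsistency rests on the printed text alone and is certain as far as that text goes. Three things are inferences: that the table is meant as conditions for treatment, that the inequality is reversed, and that 6 seconds is the intended cut-off. The argument about the entry limit assumes equal item weights in the CTP score, and is needed only to show that the limit does not fill the gap.

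The cell applies to subjects with CTP score 7, an unstated share of the 20 to be enrolled. Nothing here supports a criticism of the primary endpoint, the sample size or the 3-of-15 rule.

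**What to change.** In section 11.0, change the CTP-B7 clotting cell to PT no more than 6 seconds above normal, or preferably to an equivalent INR ceiling so that the row uses one measure. The clinical team should confirm the cut-off, because the documents give neither the intended value nor a conversion from PT to INR. Add a caption saying that the table lists conditions to start or continue treatment.

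The cost is a short amendment covering one cell and one caption. It needs no additional subjects, tests or data, and no change to the analysis.
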